3.9.1.2 Grading of AEs

AEs will be assessed according to the Common Terminology Criteria for Adverse Events (CTCAE) version 4.0.3.

The CTCAE represents a comprehensive grading system for reporting the acute and late effects of cancer treatments. CTCAE v4.0.3 grading is by definition a 5-point scale generally corresponding to mild, moderate, severe, life threatening, and death.

If CTCAE grading does not exist for an adverse event, grades 1 – 4 corresponding to the severity of mild, moderate, severe, and life-threatening will be used. CTCAE grade 5 (death) will not be used in this project; if an AE results in death it will be documented in the outcome (“fatal”). Information on deaths will also be collected on the ‘Death’ CRF.

3.9.1.3 General rules for AE Reporting

AE summaries will include all AEs starting on or after study Day 1 (i.e. on or after the day of the first intake of study treatment) and starting no later than 30 days after the last administration of study treatment (see [Section 2.1.5](#)). All AEs will be listed. AEs starting prior to study Day 1 and AEs starting later than 30 days after the last treatment date will be flagged in the listings.

AEs will be summarized by presenting the number and percentage of patients having at least one AE, having at least one AE in each primary system organ class, and for each preferred term using MedDRA coding. A subject with multiple occurrences of an AE will be counted only once in the AE category.

Separate AE summaries will be presented by primary system organ class, preferred term, and maximum grade . A patient with multiple grades for an AE will be summarized under the maximum grade recorded for the event. AE with missing CTCAE grade will be included in the ‘All grades’ column of the summary tables.

In AE summaries the primary system organ class will be presented alphabetically and the preferred terms will be sorted within primary SOC in descending frequency. The sort order for the preferred term will be based on their frequency in the ribociclib arm.

The frequency of grade 3 and 4 AEs will be summarized separately.

Any information collected (e.g. grades, relationship to study treatment, action taken etc.) will be summarized and listed as appropriate.

3.9.1.4 AE summaries

The following adverse event summaries will be produced:

- Summary of deaths and adverse events
- AEs, irrespective of causality, by primary system organ class, preferred term and maximum grade
- AEs with suspected relationship to study treatment by primary system organ class, preferred term and maximum grade
- Most common grade 3-4 adverse events, irrespective of causality, by preferred term and maximum grade (greater than x% in either arm)
- Adverse events, irrespective of causality, by primary system organ class and maximum grade
- Adverse events, irrespective of causality, by preferred term and maximum grade

- Adverse events with suspected relationship to study treatment by preferred term and maximum grade
- Grade 3 or 4 AEs, irrespective of causality, by primary system organ class, preferred term and maximum grade
- Grade 3 or 4 AEs with suspected study treatment relationship by primary system organ class, preferred term and maximum grade
- On treatment deaths, by preferred term
- All Deaths(on-treatment + post-treatment), by primary system organ class and preferred term
- Serious AEs, irrespective of causality, by primary system organ class, preferred term and maximum grade
- Serious AEs with suspected relationship to study treatment, by primary system organ class, preferred term and maximum grade
- AEs leading to discontinuation, irrespective of causality, by primary system organ class, preferred term and maximum grade
- AEs requiring dose adjustment , irrespective of causality, by primary system organ class, preferred term and maximum grade
- AEs requiring treatment interruption, irrespective of causality, by primary system organ class, preferred term and maximum grade
- AEs requiring additional therapy, irrespective of causality, by primary system organ class, preferred term and maximum grade
- Non-serious AEs (at least x% incidence rate in either treatment arm) by primary system organ class and preferred term.
- Serious and non-serious adverse events with number of occurrences (an occurrence is defined as >1 day between start and prior end date of record of same preferred term)
- On-treatment deaths and SAEs with fatal outcome, by SOC and PT

AEs of special interest will also be summarized. See [Section 3.9.1.5](#) for the grouping details.

3.9.1.5 Grouping of AEs of special interest

An adverse event of special interest is a grouping of adverse events that are of scientific and medical concern specific to ribociclib. These groupings are defined using MedDRA terms, SMQs (standardized MedDRA queries), HLGs (high level group terms), HLTs (high level terms) and PTs (preferred terms). Customized SMQs (Novartis MedDRA queries, NMQ) may also be used. A NMQ is a customized group of search terms which defines a medical concept for which there is no official SMQ available or the available SMQ does not completely fit the need. It may include a combination of single terms and/or an existing SMQ, narrow or broad. For each specified AESI, the number and percentage of patients with at least one event of the AESI occurring during the on-treatment period will be summarized.

Summaries of these AESIs will be provided by treatment arm, (specifying grade, SAE, relationship, leading to treatment discontinuation, leading to dose adjustment/interruption, etc.).

A Case Retrieval Sheet (CRS) with the exact composition of the AE groupings is to be used to map reported AEs to the AESI groupings. This file may be updated (i.e. it is a living document) based on review of accumulating trial data, and therefore the groupings are also subject to potential change. [Table 3-7](#) provides the latest groupings at the time of the finalization of the SAP, from the CRS dated 13Dec2016. The most up-to-date version of the CRS will be used at the time of the analysis.

Table 3-7 AESI groupings

AESI grouping	MedDRA category
Anemia	SMQ
Diarrhea	SMQ
Hepatobiliary toxicity	SMQ
Infections	SMQ and SOC
Leukopenia	HLT
Nausea, emesis	HLT
Neutropenia	HLT and PT
Pneumonitis, interstitial lung disease	SMQ
Pulmonary embolism	SMQ and HLT
QTc prolongation	SMQ
Renal impairment	SMQ
Reproductive toxicity	SMQ
Thrombocytopenia	SMQ

3.9.2 Laboratory data

On analyzing laboratory data, data from all sources (central and local laboratories) will be combined. The summaries will include all laboratory assessments collected no later than 30 days after the last administration of study treatment. All laboratory assessments will be listed and those collected later than 30 days after the last treatment date will be flagged in the listings.

Laboratory data will be classified (by biostatistics/statistical reporting) into CTC grades according to the NCI CTCAE v4.0.3. The calculation of laboratory CTC grades will be based on the observed laboratory values only; clinical assessments will not be taken into account. The criteria to assign CTC grades are given in Appendix 1.

For laboratory tests where grades are not defined by CTCAE, results will be graded by the low/normal/high classifications based on laboratory normal ranges.

The following summaries will be produced for the laboratory data (by laboratory parameter):

- Number and percentage of patients with each CTC grade as their worst post-baseline value (regardless of the baseline status). Each patient will be counted only for the worst grade observed post baseline.
- Shift tables using CTC grades to compare baseline to the worst post-baseline value will be produced for hematology and biochemistry laboratory parameters with CTC grades.

- For laboratory parameters where CTC grades are not defined, shift tables to the worst post-baseline value will be produced using the low/normal/high classifications based on laboratory reference ranges.
- Number and percentage of patients meeting categorical liver function test criteria, including ALT, AST and ALT/AST (>3x, 5x, 8x, 10x, 20x ULN), Total Bilirubin (>1x, 2x ULN), ALP (>1.5x, 2x, 3x, 5x, 8x, 10x ULN), combined categories of ALT/AST and total bilirubin (e.g., ALT/AST>3x ULN & total bilirubin > ULN) as well as potential Hy's Law criteria (ALT or AST > 3 x ULN and TBIL > 2 x ULN and ALP < 2 x ULN). For the combined categories, the assessments need not be concurrent, i.e. patients are counted based on their most extreme value for each parameter (highest in the case of ALT, AST and TBIL; lowest in the case of ALP).
- Box plots of laboratory values by scheduled time point and treatment arm.

The following listings will be produced for the laboratory data:

- Listing of patients with CTC grade 3 or 4 laboratory abnormalities;
- Listing of all laboratory data with values flagged to show the corresponding CTC grades and the classifications relative to the laboratory reference ranges.

Time to first occurrence of grade 2 or worse laboratory toxicity and time to first occurrence of grade 3 or worse laboratory toxicity will be performed for (i) neutropenia and (ii) ALT/AST. Median time to first occurrence and 95% CI will be provided based on the Kaplan-Meier method. In addition, Kaplan-Meier plots will be generated.

Time to first occurrence of grade X or worse laboratory toxicity is defined as the time from the start of treatment to the start date of the first incidence of grade X or worse laboratory toxicity, i.e. time in days is calculated as (start date of first occurrence) – (date of first dose of study treatment) + 1. A patient will be censored if:

- The patient did not report any post-baseline grade X or worse event on or before the analysis cut-off date.
- The patient discontinued treatment without reporting any grade X or worse event up to 30 days after study treatment discontinuation.
- The patient died without reporting any grade X or worse event.
- The patient received a new anticancer therapy before reporting any grade X or worse event.

The censoring date will be the earliest of the following dates: end of treatment + 30 days, analysis cut-off, new anti-cancer therapy start date, death date and last non-missing assessment for the lab parameter. Note that patients who have grade X or worse toxicity at baseline or missing baseline evaluation will be excluded from this analysis.

In addition, the median time to first occurrence for the subset of patients who experienced the event of interest will be calculated. Simple descriptive statistics, median, min and max as well as 25th percentile and 75th percentile, will be presented.

Duration of grade X or worse laboratory toxicity may also be summarized. Duration of grade X or worse event is calculated as:

(Date when the grade of the event decreases to below X) – (date of onset of grade X or worse event) + 1

For patients experiencing any grade X or worse event, the duration of the first such event will be summarized using the Kaplan-Meier method. Median duration and 95% CI will be presented. In addition, Kaplan-Meier plots will be generated.

A patient will be censored for the duration of grade X or worse event, if:

- The patient dies without reporting a decrease to below grade X
- The patient receives a new anticancer therapy before reporting a decrease to below grade X
- The patient discontinues from the study treatment without reporting a decrease to below grade X up to 30 days after study treatment discontinuation
- The patient is still ongoing at the analysis cut-off date without reporting a decrease to below grade X

The censoring date is the earliest of the following dates: end of treatment + 30 days, analysis cut-off, new anti-cancer therapy start date, death date and last non-missing assessment for the lab parameter.

Urinalysis

The following parameter will be summarized using shift table to compare baseline to the worst-post baseline values: urine bilirubin dipstick, urine blood dipstick, urine glucose dipstick, urine ketones dipstick, urine leukocyte dipstick, and urine nitrate dipstick. For all these parameters, both negative and trace are considered as normal and the more pluses the worse. The urine pH dipstick will be summarized using shift table with low/normal/high classifications based on laboratory reference ranges.

3.9.3 Vital signs

Vital signs assessments are performed in order to characterize basic body function. The parameters expected to be collected include: height, weight, body temperature, heart rate, and systolic and diastolic blood pressure.

The criteria for clinically notable abnormalities are defined as follows:

Clinically notable elevated values

- Systolic BP: ≥ 180 mmHg and an increase ≥ 20 mmHg from baseline
- Diastolic BP: ≥ 105 mmHg and an increase ≥ 15 mmHg from baseline.
- Body temperature: $\geq 39.1^{\circ}\text{C}$
- Heart rate: ≥ 120 bpm with increase from baseline of ≥ 15 bpm

Clinically notable below normal values

- Systolic BP: ≤ 90 mmHg and a decrease ≥ 20 mmHg from baseline
- Diastolic BP: ≤ 50 mmHg and a decrease ≥ 15 mmHg from baseline
- Body temperature: $\leq 35^{\circ}\text{C}$
- Heart rate: ≤ 50 bpm with decrease from baseline of ≥ 15 bpm

The following summaries will be produced for each vital sign parameter:

- Summary statistic for change from baseline to the worst post-baseline value (in both directions, i.e. from baseline to highest post baseline and from baseline to lowest post baseline value).
- Number and percentage of patients with at least one post-baseline vital sign abnormality (in both directions, i.e. both elevated and below normal values).

In addition, the following two listings will be produced by treatment arm:

- Patients with clinically notable vital sign abnormalities.
- All vital sign assessments will be listed by patient and vital sign parameter.

In both listings, the clinically notable values will be flagged and also the assessments collected later than 30 days after the last treatment date will be flagged.

3.9.4 ECG

All analyses of ECG data will be based on the average of all available replicate ECGs assessed at each time point for each patient. For unscheduled assessments, 15-minute windows will be applied to group assessments for averaging.

ECG data will be summarized by presenting summary statistics of the raw data and change from baseline by treatment arm and time point. The following parameters will be assessed: QT, QTcF, QTcB, PR, and QRS intervals in msec, heart rate (bpm), and the overall interpretation if clinically significant abnormalities are present.

The number and percentage of patients with notable abnormalities will be summarized. Summary statistics and shift tables will be presented. Individual listings will be provided by subject.

Table 3-8 Clinically notable ECG values

ECG parameter (unit)	Clinically notable criteria
QT, QTcF, QTcB (ms)	New > 450
	New > 480
	New > 500
	Increase from Baseline > 30
	Increase from Baseline > 60
PR duration (ms)	Increase > 25% from baseline and to PR duration > 200 New > 200
QRS duration (ms)	Increase > 25% from baseline and to QRS duration > 110 New > 110
Heart Rate (bpm)	< 50 and decrease from Baseline of > 25%
	> 100 and increase from Baseline of > 25%

A newly occurring ECG abnormality is defined as an abnormal post-baseline ECG finding that is not present at baseline. Baseline is defined as the average of the last replicate ECG measurements taken

on or before treatment start date. The percentage of patients having notable ECG interval values is based on the number of patients at risk for the change with a value at baseline and post-baseline.

Time to grade 2 or worse QT prolongation will be analyzed using the Kaplan-Meier method and the median time to grade 2 or worse QT prolongation will be presented along with a 95% confidence interval if there are sufficient numbers of events for each treatment group.

In addition, the median time to event for the subset of patients who experienced grade 2 or worse QT prolongation will be calculated. Simple descriptive statistics, median, min and max as well as 25th percentile and 75th percentile, will be presented.

Note that patients who have grade 2 or worse toxicity at baseline or missing baseline evaluation will be excluded from these analyses.

ECG by dose group will also be explored as described in [Section 3.10.4.3](#).

3.9.5 Cardiac imaging (MUGA / ECHO)

Shift tables comparing baseline to worst post-baseline cardiac imaging (MUGA or ECHO) overall interpretation will be provided. Percentages will be based on all patients in the Safety set.

Note: If there is any change in the methodology used throughout the study compared to baseline, the post-baseline values for which the methodology differs from baseline will be discarded in the tables presenting comparisons to baseline.

Descriptive statistics of the left ventricular ejection fraction (LVEF) at baseline, worst post-baseline value and change from baseline to worst post-baseline value will be provided.

A listing of patients with newly occurring clinically significant abnormality will be produced by treatment arm.

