- Section 6.3.1.4.1, renumbered as 6.3.1.4.3. Word “planned” changed to “ongoing” regarding the status of the human ADME study.
- Section 6.4: Modified for better clarity
  - Section 6.4.4: Additional clarification added regarding concomitant medication associated with menopausal status.
- Section 6.5.3, added the words “for safety reasons” and “safety reasons for” in order to align protocol and IRT language regarding the specific reasons for emergency patient unblinding.
- Section 7, to include Table 7-1, Table 7-2:
  - Minor modifications to screening windows
  - Further clarification of Cycle 1 Day 1 assessments
  - Removal of Thyroid T3 and TSH
  - Addition of monthly urinalysis collection
  - Further clarification of Local FSH and/or Estradiol for eligibility
  - Addition of “Fluid/Tissue Collection” in the Tumor Assessments, as clinically indicated.
  - Revision of window regarding whole body bone scan: change from within 28 days to within 42 days of randomization
  - Further clarification on ECG assessments
  - Removal of ECHO/MUGA after screening, and addition of ECHO/MUGA collection at End of Treatment (EOT).
  - Clarification of Serum Pregnancy test and Urine Pregnancy Test
  - [REDACTED]
  - Clarification regarding study treatment discontinuation
  - Clarification regarding tumor assessment schedule following randomization
- Section 7.1.2: Minor modifications to reflect screening windows, removal of thyroid testing
- Section 7.1.5: Modified for better clarity on the definition of study treatment discontinuation.
- Section 7.1.6: Modified for better clarity regarding follow-up period.
- Section 7.1.8 has been added to better clarify patient withdrawal of consent and process to follow by investigators.
- Section 7.2.1: Modified for better clarity; revision of whole body bone scan screening window
- Section 7.2.2.6, Table 7-5, Table updated to reflect the new ECG frequency and additional recommendations given with regards to ECG assessment in case of abnormalities and cardiologist consultation.
- Section 7.2.4: Modified for better clarity
- Table 7-14, 7-15: Screening window modified to reflect Table 7-1.

[figure not shown]
- Section 9.3.5 modified to clarify which local lab results to collect in the CRF

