### **6.1.5 Treatment duration**

Patients may continue study treatment until disease progression (radiologically documented according to RECIST 1.1), or until discontinuation of study treatment due to any other reason (see [Section 7.1.5](#)).

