FSH (Local at screening for eligibility)	S	5.2	x												
FSH	D	7.2.2.5.5		x											
Plasma estradiol (Local at screening for eligibility)	S	5.2	x												
Coagulation	D	7.2.2.5.3	x			x		x				x			
Urinalysis	D	7.2.2.5.4	x			x		x				x			
Tumor Assessment															

[figure not shown]
Visit name	Category	Reference to Protocol Section	Screening Phase		Treatment Phase								Post-treatment Phase	
			Cycle 1	Cycle 2	Cycle 3	Subsequent cycles	End of study treatment (EOT) within 15 days from the last dose	Safety follow up EOT + 30 days	Efficacy Follow up	Survival Follow up (Every 12 weeks)				
Treatment days			-28 to -1	-14 to -1	1	15	1	1	15	16	1			N/A
Tumor Assessment	D	7.2.1.1	x		Every 8 weeks during the first 18 months, then every 12 weeks until 36 months, and thereafter as clinically indicated until disease progression, death, withdrawal of consent, loss to follow-up, subject/guardian decision, and at EOT (If PR/CR is reported, confirmation of response is required; confirmatory assessment should be performed ≥ 4 weeks after response is first documented.)								x	
Fluid/Tissue collection results (if available)	D	7.2.1	As clinically indicated until disease progression											
Whole body bone scan	D	7.2.1	x (within 42 days prior to randomization)	As clinically indicated										
Safety														
Triplicate ECG (standard 12-lead)	D	7.2.2.7.1	x	x	x	x	x	x	x	x	x	x	x	x
ECHO or MUGA with EF	D	7.2.2.7.2	x	As clinically indicated								x		
Serum Pregnancy Test (Local)	D	7.2.2.5.5	x									X		

Visit name	Category	Reference to Protocol Section	Screening Phase		Treatment Phase							Post-treatment Phase			
			Screening	Screening	Cycle 1	Cycle 2	Cycle 3	Subsequent cycles	End of study treatment (EOT) within 15 days from the last dose	Safety follow up EOT + 30 days	Efficacy Follow up	Survival Follow up (Every 12 weeks)			
Treatment days			-28 to -1	-14 to -1	1	15	1	1	15	16	1				N/A
Urine Pregnancy test	D	7.2.2.5.5			x		x	x			Every third cycle				
Concomitant medications/procedures	D	6.4	x		Continuous							x	x		
Adverse events	D	8	x		Continuous							x	x		
End of Phase Disposition	D	7										x		x	

Visit name	Category	Reference to Protocol Section	Screening Phase		Treatment Phase							Post-treatment Phase		

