3.7.5 Cardiac imaging (MUGA / ECHO)

Shift tables comparing baseline to worst post-baseline cardiac imaging (MUGA or ECHO) overall interpretation will be provided. Percentages will be based on all patients in the Safety set.

Note: If there is any change in the methodology used throughout the study compared to baseline, the post-baseline values for which the methodology differs from baseline will be discarded in the tables presenting comparisons to baseline.

Descriptive statistics of the left ventricular ejection fraction (LVEF) at baseline, worst post-baseline value and change from baseline to worst post-baseline value will be provided.

A listing of patients with newly occurring clinically significant abnormality will be produced by treatment arm.

ECG data of patients with abnormal values starting or worsening during the cross-over on-treatment period will be listed separately.

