2.3.2 Safety set

The Safety Set consists of all patients who received at least one dose of any component of study treatment. Patients will be analyzed according to the treatment actually received. Treatment

actually received refers to the treatment the patient was randomized to, unless the alternative treatment was received throughout the trial.

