3.16 Sample size calculation

The assumption of median PFS of 9 months in the control arm (tamoxifen/NSAI + goserelin) for sample size calculation is based on the meta analysis of 4 trials in premenopausal advanced breast cancer treated with combination of tamoxifen and luteinizing hormone-releasing hormone agonist (Klijn 2001) and the results of the letrozole study in breast cancer patients (Mouridsen 2003). It is expected that the addition of ribociclib will result in 33% reduction in the hazard rate (corresponding to an increase in median PFS to 13.4 months assuming PFS has an exponential model assumption).

If the true hazard ratio is 0.67 (under alternative hypothesis), a total of 329 PFS events provide 95% power at a one-sided overall 2.5% level of significance to reject the null hypothesis (hazard ratio=1) using a log-rank test. Considering a recruitment period of approximately 18 months at a uniform rate of 33 patients/month, 600 patients will need to be randomized to the two treatment arms in a 1:1 ratio. Assuming about 10% patients will be lost to follow-up for PFS, a total of 660 patients will need to be randomized. Given the above assumptions, it is estimated that the 329th PFS event will be observed at approximately 22 months from the date of first patient randomized in the study. The sample size calculation was conducted with software package East 6.3.

It is expected that both the endocrine treatment types (tamoxifen and NSAI) will have an adequate number of patients randomized for the respective subgroup analyses. However, this will be monitored closely in a blinded fashion and the protocol may be amended for further randomization in a given group if enrollment is found to be slow.

[figure not shown]
Audit size calculation for BIRC assessment of PFS

The audit size of the sample-based BIRC assessment will be 40% of all randomized patients. Based on the audit size calculation approach proposed by Dodd et al (2011), assuming investigator and BIRC assessments are similar and the estimated log of investigator-based HR is -0.40 (i.e. HR=0.67), the audit size of 40% will ensure that the upper bound of a one-sided 95% CI for BIRC-based log-hazard ratio has 86% probability of being below zero (i.e. HR < 1) if the correlation between investigator assessment and BIRC assessment is 0.7 (the estimated

correlation based on data from the BELLE-2 [CBKM120F2302] study in metastatic breast cancer).

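### Cardiac-imaging shift percentages are divided by the whole Safety Set although routine scans occur only at screening and end of treatment, so they understate the rate among assessed patients, probably more on ribociclib

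*SAP*

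**What the plan says.** **Schedule.** In Protocol Table 7-1a (Section 7.1) the row "ECHO or MUGA with EF" is marked at screening and at EOT. Between the two, scans are done only when clinically indicated. Table 7-1b gives crossover cycles the same as-needed rule. The Amendment 1 change list records that scheduled on-treatment scans were dropped and the EOT scan added, so this schedule was in force well before the primary-analysis SAP.

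**Denominator.** Section 3.9.5 of the primary-analysis SAP plans shift tables of the overall imaging interpretation, baseline against worst post-baseline, and says "Percentages will be based on all patients in the Safety set". Section 3.7.5 of the final-CSR SAP uses the same sentence.

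**Who is in that set.** Section 2.3.2 of the primary-analysis SAP: "The Safety Set consists of all patients who received at least one dose of any component of study treatment". The final-CSR SAP also asks for a post-baseline safety assessment, but a statement that the patient had no adverse event is enough. Neither definition requires a scan.

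**Off-method scans.** If the imaging method changes, "the post-baseline values for which the methodology differs from baseline will be discarded in the tables presenting comparisons to baseline". The denominator is not adjusted for this.

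**A different rule next door.** In the ECG sections (3.9.4 and 3.7.4) the percentage with notable interval values "is based on the number of patients at risk for the change with a value at baseline and post-baseline".

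**The concern.** A patient still on treatment at the data cut-off has no scheduled post-baseline ejection fraction. She can add to the denominator but, unless scanned for cause, not to the numerator. A percentage built this way mixes how often an abnormality was found with how often anyone looked.

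The mixing need not be equal between arms. Protocol 6.1.5 lets treatment run until progression, and the trial is designed on the expectation that ribociclib delays progression. At a given cut-off more ribociclib patients should therefore be short of their EOT scan. A reader comparing the two columns could take a difference in measurement for a difference in cardiac risk, and the likely direction is to make ribociclib look better than it is.

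**Working it through.** **Inputs.** From the sample size section (Protocol 10.8, SAP 3.16): median PFS 9 months on control and 13.4 on ribociclib (hazard ratio 0.67), exponential; 600 patients 1:1, uniform accrual over 18 months; 329 PFS events at about month 22. Assumption: a PFS event stands in for reaching EOT.

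**Step 1: reproduce the plan's figure.** The SAP states that "a total of 329 PFS events provide 95% power at a one-sided overall 2.5% level of significance".
- Schoenfeld: 4(1.960 + 1.645)² / (ln 0.67)² gives 325 events. Freedman gives 333. Both lie close to 329.
- Power at 329 events: 95.3%.

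**Step 2: share past EOT at month 22.** Follow-up is uniform on 4 to 22 months, so the share with an event is 1 − (e^(−4L) − e^(−22L)) / (18L).
- Placebo, L = ln 2 / 9 = 0.0770: 1 − (0.735 − 0.184)/1.386 = 0.602.
- Ribociclib, L = 0.67 × 0.0770 = 0.0516: 1 − (0.814 − 0.321)/0.929 = 0.470.
- Check: 300 × 0.602 + 300 × 0.470 is about 322 events at month 22, and the 329th falls at 22.4 months, so the model matches the plan's timing.

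**Step 3: effect on the printed percentage.** Printed rate = rate among assessed × share assessed. With an illustrative 5% among assessed patients in both arms and no ongoing patient scanned:
- placebo 5% × 0.602 = 3.0%; ribociclib 5% × 0.470 = 2.35%; ratio 0.78.
- Conversely, a ribociclib:placebo ratio of 0.602/0.470 = 1.28 among assessed patients would print as 1.0.

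**Step 4: range.**

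| Change in assumption | Placebo assessed | Ribociclib assessed | Ratio |
|---|---|---|---|
| None | 60.2% | 47.0% | 0.78 |
| 25% of ongoing patients scanned | 70.2% | 60.3% | 0.86 |
| 50% of ongoing patients scanned | 80.1% | 73.5% | 0.92 |
| 20% per year non-progression discontinuation, both arms | 67.5% | 57.1% | 0.85 |

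If only 60 to 100% of EOT scans are done, equally by arm, both shares fall and the ratio does not move.

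**Step 5: later counts.** The amendment summaries give 89 ribociclib and 46 placebo patients on treatment in July 2019, and 79 and 35 in January 2020. Taking 672/2 = 336 per arm (exact arm sizes are not given), the shares off treatment are 73.5% against 86.3%, then 76.5% against 89.6%. The ratio is 0.85 at both dates: same direction, smaller gap.

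**The case against.** Several objections have force.

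- **Shown as normal?** A reader might infer that patients without a usable scan are presented as having no abnormality. The documents do not say so. Off-method values are discarded, and the table layout is left to shells that are not part of these documents. A missing column may exist. It would reveal the gap, but percentages on the full set would still be diluted.
- **The ECG precedent.** It is tempting to say the sponsor already uses the stricter rule for ECG shift tables. It does not: that denominator is stated for notable interval values, and no denominator is given for the ECG shift tables. The contrast is relevant but is not a template.
- **0.78 as the bias.** That is the extreme of the range. It supposes that nobody still on treatment is scanned, although scans for cause are allowed and symptomatic patients are the likeliest to have them.
- **Switching the denominator as a cure.** Suppose a 5% true rate in both arms, and that half of abnormal ongoing patients and no normal ongoing patients are scanned. The Safety Set rule prints 4.0% placebo and 3.7% ribociclib (ratio 0.92). The assessed-only rule prints 4.0/61.2 = 6.5% and 3.7/48.3 = 7.6% (ratio 1.16), both above 5%. Conditioning on having been scanned carries its own selection bias, so replacing one percentage with the other is not justified.
- **Low stakes.** The same section plans LVEF at baseline, worst value and change, plus a by-arm listing of new clinically significant abnormalities. Protocol 7.2.2.7.2 sends clinically significant findings to the adverse event form, and so to the AE summaries. None of these uses the disputed denominator, and no test is planned on the table.

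What remains is that the printed percentages cannot be interpreted without knowing how many patients were assessed in each arm, and neither SAP asks for that number here.

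**Conclusion.** The concern holds as a minor reporting weakness in one descriptive table. That the percentages understate the rate among assessed patients is arithmetic, whenever some Safety Set patients lack a valid post-baseline scan. That they do so more on ribociclib is an inference: it rests on treatment to progression, the planned hazard ratio of 0.67 and the use of PFS events as a proxy for EOT, and the later on-treatment counts agree with it. Reversing it through discontinuation would take an excess non-progression hazard on ribociclib of about 0.0770 − 0.0516 = 0.025 per month (about 26% per year); clearly more on-treatment scanning in that arm could also do it.

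At the planned primary cut-off the distortion of equal rates is a ratio of about 0.78 to 0.92, depending on how many ongoing patients are scanned. It is smaller by the final CSR. A reader might go further and conclude that the plan hides a cardiac effect of ribociclib. The documents do not support that, because the LVEF change statistics, the abnormality listing and the AE summaries are untouched.

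**What to change.** In both SAPs (3.9.5 and 3.7.5), for each arm:

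- show the number of patients with a baseline and at least one valid post-baseline assessment by the same method;
- report patients with no valid post-baseline value as a separate category, including those whose only scans were discarded for a change of method;
- give the shift percentages on the assessed number beside the Safety Set percentages;
- add a footnote that EOT and clinically indicated scans are a selected subset, so neither percentage is an unbiased estimate of risk.

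The cost is a sentence or two in each SAP and one extra column or set of rows. No new data are needed. The assessed-only percentages will be larger and less precise, and may overstate risk where scans were prompted by symptoms, which is why they should sit beside the existing percentages and not replace them.
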